## BACKGROUND AND SIGNIFICANCE

### Cancer-Related Sleep Disturbance

Cancer-related sleep disturbance is clinically significant difficulty falling asleep or staying asleep that is distressing to patients or causes daytime dysfunction and is caused, worsened, or perpetuated by cancer or treatment for cancer. It is similar to primary insomnia, understood to stem from a precipitating event that temporarily causes acute sleep disturbance which is perpetuated by behavioral changes to patients' sleep habits and environment, as well as cognitive factors. An important difference between cancer-related sleep disturbance and primary insomnia is that cancer survivors experience unique precipitating and perpetuating factors that are not experienced among the general, healthy population. For example, healthy individuals have some underlying predisposing factors for insomnia, develop acute insomnia due to precipitating factors, and this continues to chronic insomnia due to behavioral and cognitive perpetuating factors. These behavioral factors are typically maladaptive strategies to account for acute insomnia (e.g., napping after work).

In contrast, cancer survivors face unique precipitating and perpetuating factors. These include the cancer itself as well as pain, nausea, and other side-effects not experienced by most others with no history of cancer. Thus, cancer-related sleep disturbance and primary insomnia differ in terms of their etiology. These differences underscore the rationale for adapting an intervention for cancer-related sleep disturbance that was specifically developed for cancer survivors. The study team has developed a collaboration with an investigator who led the development of just such an intervention. This intervention has demonstrated efficacy towards reducing sleep disturbance and impacting immune function.

### Need for Spanish-Language Intervention for Cancer-Related Sleep Disturbance

Although cancer-related sleep disturbance is largely overlooked among Hispanic cancer survivors, large epidemiologic studies among cancer-free individuals have demonstrated that Hispanics have worse sleep disturbance than non-Hispanic Whites, especially older Hispanics. Despite this documented disparity, there is an acute lack of behavioral interventions for Spanish-speaking cancer survivors. For example, although numerous specialized courses are available in English to train behavioral therapists to provide first-line therapy for insomnia, many therapists are unable to pay the travel and registration fees. Numerous English-language manuals exist that enable behavioral therapists to provide first-line therapy for insomnia, we are unaware of a single manual that Spanish-speaking behavioral therapists in the USA can follow. Moreover, we are unaware of a single Spanish-language course that provides training to administer this treatment. The numerous negative biological, emotional, and psychological consequences of sleep disturbance underscore that Spanish-speaking cancer survivors are at a distinct disadvantage because they are largely unable to receive first-line therapy for cancer-related sleep disturbance.

### The Current Study

The current project will leverage an existing intervention that has demonstrated efficacy among cancer survivors to create and test a Spanish-language behavioral intervention in a pilot randomized clinical trial. We will first gather qualitative data from patients, caregivers, and providers to determine the best mode of delivery of this new intervention (e.g., in person, in print, via Internet). We will then adapt the existing intervention into a Spanish-language intervention. Lastly, we will test this new intervention in a sample of 30 Spanish-speaking breast cancer survivors using a randomized controlled design. Data will be used to address the following aims:

### SPECIFIC AIMS

**Aim 1: Gather qualitative data from cancer survivors, caregivers, and clinicians to determine the best modality to deliver the new intervention.**

**Aim 2: Develop a new behavioral intervention to reduce cancer-related sleep disturbance in Spanish-speaking cancer survivors.** Hypothesis 1: We hypothesize that we will be able to adapt an existing, written, and manualized behavioral intervention and culturally target this intervention for Spanish-speaking cancer survivors.

**Aim 3: Pilot test the new intervention for feasibility, acceptability, and preliminary efficacy in a sample of N=30 participants.** Hypothesis 2: We hypothesize that participants randomized to receive the new intervention will

report greater pre- to post-treatment reductions in cancer-related sleep disturbance than participants randomized to a wait-list control condition.

**Aim 4: Explore changes in sleep disturbance during the COVID-19 pandemic which may influence future trials of the new intervention.**

## RESEARCH DESIGN AND METHODS

**Aim 1: Gather qualitative data from cancer survivors, caregivers, and clinicians to determine the best modality to deliver the new intervention.**

### Overview

The qualitative component will begin by inviting 10 cancer survivors, 10 survivors' caregivers, 5 clinicians, and 5 cancer support group leaders to participate in individual interviews about how best to deliver a cancer-related sleep disturbance intervention. We hypothesize that qualitative interviews with patients, providers, and caregivers will demonstrate that Spanish-speaking cancer survivors in Puerto Rico with cancer-related sleep disturbance will prefer to receive this intervention in group sessions and printed materials rather than via the Internet or via printed materials only.

**Role of PIs:** [name] will oversee all aspects of Aim 1 in close collaboration with [name], who will supervise identification of potentially eligible participants, recruitment of participants, and collection of qualitative interview data. Drs. [name] and [name] will analyze qualitative data together. Participants will be recruited only within the Southern Puerto Rico area.

### Eligibility Screening and Recruitment

Eligible cancer survivors (n=10) will: a) be  $\geq$  18 years old, b) be able to speak and read Spanish, c) have no documented or observable disabilities that would preclude participation in the qualitative interviews, d) be required to have completed primary treatment for breast cancer, and e) report clinically significant sleep disturbance (i.e.,  $\geq$  8 on the Insomnia Severity Index). Eligible caregivers (n=10) will be required to be  $\geq$  18 years old and a caregiver for a friend or relative who meets eligibility criteria to participate as a survivor. Eligible clinicians (n=5) will be required to be  $\geq$  18 years old and be medical providers for cancer survivors. Eligible cancer support group leaders (n=5) will be required to be  $\geq$  18 years old and be leaders of cancer support groups in the Southern Puerto Rico area.

Potential cancer survivor participants will be recruited from medical clinics and cancer support groups in the Southern Puerto Rico area. Potential participants will be approached in a HIPAA-compliant manner by a trained research associate in person and/or via telephone. Those who are approached through medical clinics will be identified in consultation with the medical team. Those who are approached through cancer support groups will be identified in consultation with the cancer support group leader(s). A Spanish-speaking study team member will determine eligibility through chart review and discussion with the medical team or cancer support group leaders, approach patients via telephone or in person, and confirm eligibility with a brief questioning of the potential participant. Participants who meet all eligibility criteria will be provided with oral and written explanations of the study and the opportunity to ask questions. Eligible and interested patients will then be invited to nominate caregivers to be approached for participation. Lastly, eligible and interested patients will be invited to provide informed consent and complete the interview or schedule an appointment to provide informed consent and complete the interview.

Potential caregiver participants will be nominated by eligible cancer survivors. Potentially eligible caregivers will be contacted in person and/or via telephone by a study team member who will describe the study, confirm eligibility, and provide an opportunity to ask questions about the study. Eligible and interested caregivers will then be either invited to provide informed consent and complete the interview or schedule an appointment to provide informed consent and complete the interview.

Clinicians and cancer support group leaders will be identified through Southern Puerto Rico area medical clinics and cancer support groups, respectively. Potentially eligible clinicians and support group leaders will be approached in person and/or via telephone by a study team member who will describe the study, provide an

opportunity to ask questions about the study, and either provide informed consent and complete the interview or schedule an appointment provide informed consent and complete the interview.

## Interviews

Survivors and caregivers will be interviewed separately by phone or in person at the location of the participant's choosing. Interviews will be aimed at identifying how best to deliver the cancer-related sleep disturbance intervention. In addition, interviews will assess patients' perceptions of: 1) medications that may impact sleep disturbance, 2) non-pharmacological interventions for insomnia (vs. pharmacotherapy), 3) need to address sleep disturbances in cancer patients, 4) when this treatment should be offered in the cancer care trajectory, and 5) what kind of professionals should offer this service. Interviewers will follow a semi-structured interview guide to be developed by Drs. [name] and [name]. Interviews are expected to last up to 30 minutes and will be audio-recorded and professionally transcribed verbatim. Clinicians and cancer support group leaders will be interviewed individually by phone or in person at a location of their choosing. Each participant will be provided a \$50 gift card after completion of the interview.

## Data Analysis

All transcripts will be entered into NVivo, a qualitative data analysis program. This software will facilitate review of transcripts by Drs. [name] and [name] to determine the consensus recommendation from patients, caregivers, clinicians, and cancer support group leaders regarding how to deliver the intervention.

### **Aim 2: Develop a new behavioral intervention to reduce cancer-related sleep disturbance in Spanish-speaking cancer survivors.**

#### Overview

The new cancer-related sleep disturbance intervention will be adapted from an existing, manualized cognitive-behavioral intervention developed by [name] to meet the needs of Spanish-speaking cancer survivors. The modality of this intervention will be selected based on input from cancer survivors, caregivers, clinicians, and cancer support group leaders in Aim 1. We hypothesize that we will be able to adapt an existing, written, and manualized behavioral intervention and culturally target this intervention for Spanish-speaking cancer survivors.

Role of Pls: [name] will oversee all aspects of Aim 2 in close collaboration with [name]. [name] will lead the development of the intervention with regular input and feedback from [name]. No participants will be recruited as part of Aim 2.

#### Intervention Development

The protocol has been amended to include the results from Aim 1. Most participants in Aim 1 recommended in-person group therapy sessions as the preferred intervention modality. Development of this manual began by translating relevant French-language text, provided by [name], into Spanish verbatim. With input from [name], Drs. [name] and [name], the text was edited to ensure 1) the language is culturally appropriate and not specific to any particular Spanish-speaking subgroup, 2) intervention materials are relevant to cancer survivors, 3) minimal burden for cancer survivors. Study investigators also re-ordered select modules from [name] original intervention to give participants time to practice sleep hygiene skills earlier on in the intervention.

The revised text was then used to develop a printed therapy manual as well as a patient manual for administration of the intervention in Aim 3.

### **Aim 3: Pilot test the new intervention for feasibility, acceptability, and preliminary efficacy in a sample of N=30 participants.**

#### Overview

A randomized, wait-list controlled trial will test the feasibility and acceptability of the new intervention in a sample of 30 breast cancer survivors. Acceptability will be assessed by examining the consent rate, obtaining verbal feedback from the group after each intervention session, and through a 10-item version of the Treatment Perception questionnaire administered to participants at the follow-up assessment. Feasibility will be determined using the number of participants who attend/receive most of the therapy sessions/content. We hypothesize that

≥ 50% of eligible participants approached to participate will sign consent and that ≥ 75% of participants will attend/receive most of the sessions/content. Intervention fidelity will be measured by a trained staff member who will listen to the recorded intervention sessions and note the completion of key intervention elements identified a priori for each session. Preliminary efficacy will be assessed with the Pittsburgh Sleep Quality Index completed before and after completing the intervention.

**Role of PIs:** [name] will oversee all aspects of Aim 3 in close collaboration with [name], who will supervise identification of potentially eligible participants, recruitment of participants, and collection of data. Drs. [name] and [name] will analyze data together. Participants will be recruited only from within Puerto Rico. The intervention sessions will take place via videoconference sessions. The day before each scheduled session a group text message will be sent reminding participants of the next session's date and time and providing a videoconference web link to join the session. It is important for participants to complete a sleep diary each morning noting various characteristics of their sleep the previous night. Because these data are an important topic of discussion during sessions, the group text message will also request participants send a reply text message with a photograph of their sleep diary.

### **Eligibility Screening and Recruitment**

Eligible breast cancer survivors (n=30) will: a) be ≥ 18 years old, b) be able to speak and read Spanish, c) have no documented or observable disabilities that would interfere with study participation, d) have completed primary treatment for breast cancer (e.g., surgery, chemotherapy, radiation), e) report clinically significant sleep disturbance (i.e., ≥ 8 on the Insomnia Severity Index), f) be at low risk of other sleep disorders that are not amenable to treatment with cognitive-behavioral therapy using the Duke Structured Interview for Sleep Disorders, and g) have access to the Internet and a digital device (e.g., smartphone) capable of using videoconference software.

Potential cancer survivor participants will be recruited from clinics, cancer support groups in the Southern Puerto Rico area, using flyers, postings to online bulletin boards, and via referral from individuals who have heard of the study. All potentially eligible survivors will be approached in a HIPAA-compliant manner by a trained research team member in person and/or via telephone. Those who are approached through medical clinics will be identified in consultation with the medical team. Those who are approached through cancer support groups will be identified in consultation with the cancer support group leader(s). Those who learn of the study via flyers, online postings, or referrals will contact the study team via the telephone number provided to them.

Eligibility will be confirmed through a brief questioning of the potential participant. Participants who meet all eligibility criteria will be provided with an explanation of the study and the opportunity to ask questions. Eligible and interested patients will be asked for an e-mail address and sent an e-mail invitation to a web link to an electronic informed consent form. Participants may also opt to be sent the invitation via a text message. Participants who follow the link and sign consent electronically will then be asked to complete a baseline assessment via the Internet. Participants will then be randomized to either the intervention or a wait-list control condition. After completing the 6-week waiting period, wait-list control group participants will be asked to complete the assessment via the Internet again before being invited to participate in an intervention group. Participants who have been sent the e-mail invitation but have not completed the informed consent form and/or baseline survey within 2 days will be contacted up to 3 times to provide any necessary clarifications and/or assistance with completing the consent form and/or survey.

### **Intervention Procedure**

Participants will be randomized to one of two arms: 1) the Spanish-language cancer-related sleep disturbance intervention or 2) wait-list control condition. Participants in the intervention group will be asked to attend videoconference group therapy sessions to be scheduled by the study team. These groups will be comprised of up to 10 participants per group and will meet weekly for 6 weeks. The groups will provide patients instruction in the following components of cognitive-behavioral therapy for cancer-related sleep disturbance:

- Sleep Education: education regarding sleep
- Sleep Hygiene: recommendations to ensure the bed and bedroom are conducive to sleep
- Sleep Restriction: consolidate time spent in bed to the actual sleep time and retrain the sleep-wake cycle

- Stimulus control: limiting non-sleep activities in bed, such as watching television, using mobile devices and re-associate the bed/bedroom with sleep
- Relapse Prevention: strategies to continue improvements made during the intervention
- Cognitive Restructuring: helping patients avoid automatic negative thoughts regarding difficulty sleeping that may make it more difficult for patients to fall asleep or stay asleep

Participants randomized to the wait-list control condition will wait 6 weeks, complete a follow-up assessment via the Internet, and then be provided access to videoconference intervention group sessions identical to those provided to intervention group participants.

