## Measures

All participants will complete the Pittsburgh Sleep Quality Index, Hospital Anxiety and Depression Scale, and Fatigue Symptom Inventory after consent (i.e., baseline) and after the 6-week intervention (i.e., post-intervention). The post-intervention assessment will also include the Insomnia Severity Index, which will have been administered as part of the screening process. Participants in the intervention group will thus complete two assessments. Participants in the wait-list control group will complete these two assessments (i.e., at baseline and after the 6-week waiting period; i.e., post-waiting) as well as a third assessment after participating in the sessions (i.e., post-intervention). Participants will be sent an e-mail and/or a text message with a link to the follow-up assessment. Participants who have been sent the survey e-mail but have not completed the follow-up survey within 2 days will be contacted up to 3 times to provide any necessary clarifications and/or assistance with completing the survey.

All participants will also complete a 10-item version of the Treatment Perception Questionnaire to assess intervention satisfaction after participating in the sessions (i.e., post-intervention). This validated measure, available in English and Spanish, assesses satisfaction with the intervention, the degree to which participants used the intervention, and the degree to which participants used specific strategies to improve their sleep. Verbal feedback will also be obtained from session participants at the end of each session to identify any terminology that was confusing, or other suggestions for improving the intervention for the future.

Each participant will be sent a \$25 gift card after completing the baseline assessment and a \$75 gift card after completing the post-intervention assessment. Participants randomized to the wait-list group will be provided a \$50 gift card after completing a third assessment after completing an additional assessment after the therapy sessions.

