## Data Analysis

The primary outcomes for this intervention are acceptability and feasibility. The study will be deemed acceptable if  $\geq 50\%$  of eligible cancer survivors who are approached agree to participate and  $> 50\%$  of intervention group participants report that, on average, they agree with positive statements about the intervention (i.e., report an average score of  $\geq 3$  on a scale of 0 to 4). The study will be deemed feasible if  $\geq 75\%$  of the intervention group participants attend at least half of the educational components of the intervention. This will be operationalized as having attended at least half of the sessions. The secondary outcome is sleep disturbance, and efficacy data will be examined at the conclusion of the intervention. Sleep disturbance will be operationalized by scores on the Pittsburgh Sleep Quality Index, sleep efficiency (the percentage of time spent in bed that is spent asleep), and the Insomnia Severity Index. The primary efficacy outcome will be the continuous measures of sleep disturbance. For secondary efficacy analyses, participants will be categorized as having sleep disturbance if 1) their Pittsburgh Sleep Quality Index score is  $\geq 5$  (for subjectively-measured sleep disturbance), 2) if their sleep efficiency is  $<85\%$  (for objectively-measured sleep disturbance), and 3) if their Insomnia Severity Index score is  $\geq 8$ . Although statistical significance will be evaluated, the primary purpose is to compute the effect size at follow-up (Cohen's  $d$ ; difference between groups divided by the pooled standard deviation). Intent-to-treat analyses will be conducted, such that all participants who are randomized will be asked to provide follow-up data at the end of the intervention period regardless of the level of use of the intervention. Participants who do not provide complete follow-up data will not need to have data imputed due to the use of mixed model analyses.

**Aim 4: Explore changes in sleep disturbance during the COVID-19 pandemic which may influence future trials of the new intervention.**

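### Does the unstated start of the controls' six-week wait bias the between-arm effect size?

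*Combined protocol and SAP*

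**What the plan says.** Under Aim 3, Eligibility Screening and Recruitment, the order is consent, baseline assessment, then allocation: "Participants will then be randomized to either the intervention or a wait-list control condition". For controls the section continues: "After completing the 6-week waiting period, wait-list control group participants will be asked to complete the assessment via the Internet again". Intervention Procedure repeats the point: "Participants randomized to the wait-list control condition will wait 6 weeks, complete a follow-up assessment via the Internet". No date or event is named as the start of that period.

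For the other arm, Intervention Procedure says: "Participants in the intervention group will be asked to attend videoconference group therapy sessions to be scheduled by the study team". It adds: "These groups will be comprised of up to 10 participants per group and will meet weekly for 6 weeks". No maximum delay to the first session is given.

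Measures sets assessments for everyone "after consent (i.e., baseline) and after the 6-week intervention (i.e., post-intervention"), and for controls "at baseline and after the 6-week waiting period; i.e., post-waiting". The Aim 3 Data Analysis section asks every randomised participant for follow-up when the intervention period closes, without defining that point for controls. It makes acceptability and feasibility the primary outcomes and sleep disturbance the secondary one. Of the efficacy analysis it says that "the primary purpose is to compute the effect size at follow-up".

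**The concern.** Two clocks run in this trial. The controls' clock has a fixed length but no stated start. The intervention arm's clock has a start that depends on when a group can be assembled. If the controls' wait begins at randomisation, which is the most natural reading of the recruitment section, any delay in forming a group lengthens only the intervention arm's interval from baseline to follow-up. The difference arises after allocation, so randomisation does not remove it.

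Hypothesis 2 compares change between arms, and Cohen's d at follow-up is the main efficacy quantity. If sleep would have changed without treatment during the extra weeks, that change would be counted as treatment effect or would mask it. The Aim 4 Overview shows that the investigators think sleep disturbance may have changed during the pandemic. At stake is the value of d carried forward to a later efficacy trial.

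A lesser, related worry is that therapy groups exist in only one arm during the comparison, and no allowance for clustering is described.

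**Working it through.** The plan states no expected d, visit window, accrual rate or drift, so there is no figure of its own to reproduce. The check asks how large the shift could be and what it is measured against.

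**Inputs from the documents.** 30 participants; groups of at most 10; six weekly sessions; a six-week wait.

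**Assumptions.** 1:1 allocation (15 per arm); accrual of 4, 6 or 10 per month at 4.33 weeks per month; each group starts when full; the wait runs from randomisation; untreated drift of 0 to 0.05 SD per week in either direction.

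**Step 1: delay to the first session.** Fifteen people in groups of at most 10 need at least 2 groups (15/10, rounded up). The mean wait in a group of g is (g − 1)/2 times the time between intervention-arm enrolments. At 6 per month, 3 per month enter that arm, one every 4.33/3 = 1.44 weeks.

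- Groups of 5+5+5: 2 × 1.44 = 2.9 weeks.
- Groups of 8+7: (8 × 3.5 + 7 × 3)/15 = 3.27; × 1.44 = 4.7 weeks.
- Groups of 10+5: (10 × 4.5 + 5 × 2)/15 = 3.67; × 1.44 = 5.3 weeks.

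The same formula at all three rates gives these mean waits in weeks:

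| Groups | 4 per month | 6 per month | 10 per month |
|---|---|---|---|
| 5+5+5 | 4.3 | 2.9 | 1.7 |
| 8+7 | 7.1 | 4.7 | 2.8 |
| 10+5 | 7.9 | 5.3 | 3.2 |

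If groups instead start on a fixed calendar every 4, 6 or 8 weeks, the mean wait is half the spacing: 2, 3 or 4 weeks. Six weekly sessions span 5 × 7 = 35 days, so each gap falls by 1 week if the follow-up link goes out straight after the last session. If a group also starts at once, the intervention interval is 1 week shorter than the controls'.

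**Step 2: shift in d.** Shift = gap in weeks × drift in SD per week. Change over the weeks that both arms share cancels.

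| Gap | 0 | 0.02 SD/week | 0.05 SD/week |
|---|---|---|---|
| 0 weeks | 0 | 0 | 0 |
| 1 week | 0 | 0.02 | 0.05 |
| 3 weeks | 0 | 0.06 | 0.15 |
| 5 weeks | 0 | 0.10 | 0.25 |
| 8 weeks | 0 | 0.16 | 0.40 |

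**Step 3: the yardstick.** With 15 per arm and d near zero, the standard error is sqrt(2/15) = 0.365. The 95% half-width is t(0.975, 28) × 0.365 = 0.748. A shift of 0.06 is 0.06/0.748 = 8% of that half-width, 0.15 is 20%, and 0.40 is 53%. The last figure needs the slowest accrual, the largest first group and the strongest drift together. At 0.05 SD per week, an untreated person would change by about 0.05 × 14 = 0.70 SD over the 6 + 8 weeks.

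**Step 4: cost of removing the gap.** Tying each control to a concurrent group's first session sets the gap to zero. In simulation under the same assumptions (Poisson accrual, blocks of 4), controls' mean wait then grows by 1.8 weeks (5+5+5 at 10 per month) to 8.0 weeks (10+5 at 4 per month).

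**Step 5: clustering.** With intracluster correlation r in one arm only, the half-width is multiplied by sqrt((DE + 1)/2), where DE = 1 + (sum of squared group sizes/15 − 1) × r. For 10+5 at r = 0.10, DE = 1 + (125/15 − 1) × 0.10 = 1.733, and the half-width is 0.748 × sqrt(2.733/2) = 0.874. At r = 0.01 it is 0.76. The point estimate is not biased.

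**The case for a change.** The strongest case for a change is this. The wait is described three times and its start is missing each time. A timing difference is systematic, does not average out over participants and is not covered by a confidence interval. Mixed models are mentioned only in connection with missing data, so nothing shows that actual assessment time is modelled. At the far corner of the assumptions the shift reaches about 0.40 SD, slightly more than one standard error (0.365). Stating the start date would cost nothing.

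Much of this stands. The omission is real, and the 0.40 corner should not be hidden behind a milder range. But bias needs three conditions together: a clock that runs from randomisation, groups that start materially late, and sleep that keeps drifting untreated over the extra weeks. The documents establish none of the three. The Aim 4 text concerns focus groups and a future trial, and gives neither size nor direction for change over a few weeks in Aim 3. Six weeks of waiting set against a six-week intervention, with all participants asked for follow-up when that period ends, points to an intended parallel. A team that schedules both the groups and the assessments can keep that parallel without an amendment.

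**Conclusion.** The text has a gap, but no change to the plan follows. The omission is a detail that the people running the trial can fill sensibly, and the documents already suggest the common frame.

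The possible shift in d is zero if randomisation is batched, if the wait is tied to a group's start, or if untreated sleep is stable. Otherwise, under assumed gaps of up to 8 weeks and drift of up to 0.05 SD per week, it is at most about 0.40 SD in either direction. In most of that range it is well below the 0.75 SD half-width that a 15-per-arm pilot carries anyway. An effect size that imprecise can inform a later trial only loosely, with or without the shift.

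The consent, satisfaction and attendance criteria that decide acceptability and feasibility do not use the interval. The one remedy that alters conduct trades a possibly absent shift for a mean 1.8 to 8.0 weeks' extra wait among about 15 controls, with some risk of losing them. That is a fair trade-off to leave as it is. Analysts can tabulate actual intervals by arm from the assessment dates when they read d, and this needs no amendment. Clustering widens the interval from 0.75 to at most 0.87 SD under the assumed correlations and changes no conclusion.

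The verdict rests on 1:1 allocation and on efficacy remaining a secondary, estimation-only aim. A confirmatory trial with the same silence would deserve a different answer.
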